## 2.8. Secondary outcomes and descriptive data

Participant characteristics such as age, sex, gender, education, marital status, race, number of people in household, height, and weight will be collected. A list of secondary outcomes is provided in Table 3.

Table 3: Secondary outcomes.

Outcome	Tool	Description
Comorbidities	Modified Charlson Comorbidity Index (CCI)	Assessed the presence of 19 comorbidities in participants. The CCI has been used in many patient populations, including knee osteoarthritis (KOA). 
Central sensitization	Mechanical Temporal Summation (TS)	A 512mN weighted probe was applied at the volar wrist opposite to the index knee. Participants were asked to rate their pain between 0 and 100  . Then, the same stimulus was applied 10 times at the rate of 1/second (guided by a metronome), and participants asked again to rate their pain. TS was defined as present when, compared with the initial trial, the participant reported increased pain following the second trial.  The validity of mechanical TS has been reported in people with KOA. 
Endogenous pain modulation	Conditioned Pain Modulation (CPM)	CPM was assessed in the following steps  : 1) at the proximal anterior shin on the unaffected knee, an ascending measure of pressure pain threshold (PPT) was evaluated; 2) at the opposite volar forearm, a conditioning stimulus in the form of forearm ischemia was applied using a blood pressure cuff and squeezing a stress ball until a pain rating of 4/10 was reached;

		
3) PPT at the anterior shin was repeated with the cuff remaining inflated.
 
4) an index was created by calculating the percent efficiency of CPM (%CPM) as PPT2/PPT1, multiplied by 100; whereby %CPM ≤ 100 indicated inefficient pain modulation. CPM testing has demonstrated good intra-session reliability.

Pain intensity	Numeric Rating Scale	
Average pain intensity in the past 24 hours, past week, and worst pain in the past 24 hours was recorded. Questions were rated on an 11-point scale where participants selected a rating between 0-10, with zero representing 'no pain' and 10 representing the 'worst imaginable pain'. The Numeric Rating Scale is reported to have excellent inter-rater reliability and acceptable validity in people with KOA.

Pain catastrophizing	Pain Catastrophizing Scale (PCS)	
The PCS is a 13-item self-reporting instrument for catastrophizing in the context of actual or anticipated pain, with higher scores indicating higher pain catastrophizing. The validity of the PCS for measuring pain catastrophizing in people with KOA has been reported.

Chronic pain self-efficacy	Self-Efficacy for Managing Chronic Disease 6-item scale (SEMCD-6)	
Higher reported scores on the SEMCD-6 indicate higher self-efficacy. The SEMCD-6 has high internal consistency with significant correlations with other health outcomes.

Anxiety and depressive symptoms	Hospital Anxiety and Depression Scale (HADS)	
Higher scores on the HADS indicate increased severity of anxiety and depression symptoms. The HADS is a brief and reliable measure of emotional

		distress in general in chronic populations  . Validity and reliability of the HADS have been previously established  .
Fear of movement	Brief Fear of Movement Scale for Osteoarthritis (BFMSO)	The BFMSO has 6 items that are derived from the Tampa Scale for Kinesiophobia (TSK) and uses a 4-point Likert scale with higher values indicating higher levels of kinesiophobia  . The BFMSO has been reported to have adequate validity  .
Knee injury and outcomes	Knee Injury and Osteoarthritis Outcome Score (KOOS)	The KOOS pain and function in daily living and QoL subscales were used to assess self-reported opinions about patients' knee and associated problems. Scores ranged from 0-100 with zero representing extreme knee problems and 100 representing no knee problems  . KOOS has adequate internal consistency and validity in people with KOA  .
Type of KOA pain	Intermittent and Constant Osteoarthritis Pain (ICOAP)	The ICOAP knee version was used to assess the different types of knee pain experienced by participants  . The ICOAP knee version has two sections: 1) 'constant pain' has 5 items that asks about pain that is present all the time, and 2) the 'intermittent pain' has 6 items that asks about pain that comes and goes. The psychometric properties of the ICOAP such as reliability and validity have been previously established  .
Other painful body parts	Body diagram	Participants were asked to indicate any other areas where they experience pain (e.g., neck, shoulders, back) on a body diagram. Body

		diagrams have shown to be a reliable method for indication of painful body parts  .
Functional leg strength	30 second sit-to-stand test	The 30 Second Sit to Stand Test was used as a performance test  . The maximum number of chair stand repetitions completed during a 30 second interval was noted. A standard chair height was used. The 30 Second Sit to Stand Test has been reported to be a reliable measure of functional leg strength and endurance  .
Brain derived neurotrophic factor (BDNF) and nerve growth factor (NGF)	Blood analysis (blood draws under fasting conditions)	Altered levels of BDNF are involved in the pathophysiology of chronic pain  . NGF has been shown to be elevated in a wide variety of chronic pain conditions including KOA  . Five ml of blood was drawn for analysis of BDNF and NGF and samples were centrifuged at 4 degrees Celsius for 10 minutes at 1000g. Collected serum was stored at -80 °C. Serum levels of BDNF, diluted 1:100, were measured using Biosensis Human/Mouse/Rat BDNF ELISA kits read on a Spectramax i3 spectrophotometer. Serum levels of NGF were measured in duplicate, after diluting 2X in Reagent Diluent, with R&D Systems Human beta-NGF DuoSet ELISA kits read on a Multiskan Go spectrophotometer.
Medication use	Survey question	Participants were asked to indicate any medication that they take on a regular schedule including prescription medications, non-prescription, over the counter, vitamins, herbal, and alternative medicines.

Perspective on knee replacement surgery	Survey question	Three questions were asked: 1. Are your knee symptoms so severe that you wish to undergo knee replacement surgery?  2. Do you think knee replacement surgery is eventually inevitable?  3. In your opinion, what factor(s) can lead to better outcomes after knee replacement surgery?
Perspectives on effectiveness of components of intervention	Survey question	Participants were asked to rank the effectiveness of the intervention components for pain management that they received. i.e. mind-body techniques, pain neuroscience education and strengthening exercises vs OA education and strengthening exercises.

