## 2.11. Analysis

Descriptive statistics will be used to report feasibility outcomes. The quantitative analysis of secondary outcomes will be by intention-

to-treat principles. Repeated measures analysis of variance (ANOVA) will be used to assess the amount of change in outcome measures and compare them between the two groups using means and 95% CIs. Similarly, within group differences will be analyzed using the paired sample's t-test and will be reported using means and 95% CIs. Where possible we will also report minimally important difference.

The transcripts of the focus group interviews will be analyzed using thematic content analysis to identify suggestions for program modification [46]. Line-by-line reading of the transcripts will be performed and thematic patterns will be explored. Once themes and patterns are identified, each meaningful segment of text will be assigned a conceptual code.

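### Temporal summation is defined only as a yes/no flag on any rise in pain, which matches none of the named analyses; the analysed form should be stated as the continuous difference in ratings (minor)

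*Combined protocol and SAP*

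**What the plan says.** Section 2.8, Table 3, central sensitization row: a weighted probe is applied once and "Participants were asked to rate their pain between 0 and 100". The stimulus is then given 10 times at one per second, and "participants asked again to rate their pain". From these two ratings the table derives only a flag: "TS was defined as present when, compared with the initial trial, the participant reported increased pain following the second trial". There is no minimum increase and no difference score.

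The next row, conditioned pain modulation, is handled differently. There "an index was created by calculating the percent efficiency of CPM (%CPM) as PPT2/PPT1, multiplied by 100", and a cut-off is added to interpret it.

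Section 2.11 on the secondary outcomes: "Repeated measures analysis of variance (ANOVA) will be used to assess the amount of change in outcome measures" and to "compare them between the two groups using means and 95% CIs"; in addition, "within group differences will be analyzed using the paired sample's t-test". It does not mention temporal summation and gives no method for a binary outcome.

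**The concern.** The only temporal summation variable that the plan defines is yes/no, and the only analyses it names are for means. Either the flag is analysed by a method meant for continuous data, or a continuous score is analysed that the plan does not define. The choice is left open until after the data are seen.

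The flag also suits the purpose poorly. The program aims to improve intrinsic pain modulation (section 1), and the third objective in section 1.1 is to explore effects on subjective and objective pain measures. Exploration of that kind looks for graded change, which a flag set at any increase records only when a participant crosses zero. A flag also cannot supply the mean and SD of summation that a later trial would need for planning.

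**Working it through.** **No stated figure to reproduce.** The documents give no prevalence, SD, effect size or power for temporal summation. The sample size of 66 rests on the follow-up rate (section 2.2) and has no bearing here. All sizes below depend on assumptions that are named.

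**Step 1: what the rule does.** Let D = rating after 10 stimuli minus rating after one. The flag is 1 if D > 0 and 0 otherwise.
- D = 40 at baseline and 5 at follow-up: flag 1 then 1, recorded as no change, although summation fell by 35 points.
- D = 1 at baseline and 0 at follow-up: flag 1 then 0, recorded as improvement, although summation fell by 1 point.

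This follows from the wording alone.

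**Step 2: information kept by the flag at one visit.** Assume D is normal and a share p has D > 0. For a small shift in D, the efficiency of the flag relative to D is φ(z_p)² / [p(1 − p)], where z_p is the normal quantile of p and φ the normal density. The last column uses 60 completers (90% of 66 = 59.4, taken as 30 per arm).

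| Share present (assumed) | φ(z_p) | Efficiency | Loss | 60 completers act like |
|---|---|---|---|---|
| 50% | 0.399 | 0.637 | 36% | 38 |
| 70% | 0.348 | 0.576 | 42% | 35 |
| 80% | 0.280 | 0.490 | 51% | 29 |
| 90% | 0.175 | 0.342 | 66% | 21 |

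For example, at 50%: 0.399² / 0.25 = 0.637.

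**Step 3: the same in terms of power.** Take 30 per arm and a shift of 0.72 SD in D at one visit. The share present in the treated arm is Φ(z_p − 0.72). Power on D is 0.796.

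| Control present | Treated present | Power on the flag |
|---|---|---|
| 50% | 23.6% | 0.567 |
| 70% | 42.2% | 0.585 |
| 80% | 54.8% | 0.549 |
| 90% | 71.3% | 0.449 |

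**Step 4: the planned comparison of change.** With two visits, the group-by-time test of a repeated measures ANOVA is the t-test on change. It was simulated with 30 per arm, 20,000 runs, a 0.6 SD shift, baseline-to-follow-up correlation 0.3 to 0.7 and 50% to 90% present. Relative efficiency is the squared ratio of the average t statistics, flag over D.
- Smallest loss: 42%, at correlation 0.3 and 70% present.
- Largest loss: 75%, at correlation 0.7 and 90% present. Power there was 0.84 on D and 0.31 on the flag.
- With no true effect, the test on the flag rejected in 4% to 5% of runs. The cost is precision and interpretation, not false positives.

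**The case against.** **The plan never says that the flag enters the ANOVA.** This stands. A reader might infer it, but section 2.11 does not mention temporal summation. Table 3 also lists medication use, a body diagram and an open question on knee replacement, for which an ANOVA cannot be meant. The defect is an unstated and mismatched outcome form, not a stated wrong analysis. Both ratings are recorded, so no data are lost.

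**The size depends on an assumed model.** This also stands. Steps 2 to 4 use normal scores and a uniform shift. In a deliberately opposite constructed case (skewed scores, treatment abolishing summation in 30% of the treated arm, status otherwise stable), the flag had 92% power and the raw difference 14%. That case is no better documented, and it does not make a cut at any increase a sensible default. It does rule out calling the flag insensitive in general.

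**Noise and ties.** A reader might infer that noise alone would label about half of participants as present. Tied ratings count as absent. With no true summation and an assumed noise SD of 3 to 10 points, the simulated share present was 42% to 46% with 1-point ratings, 26% to 40% with ratings rounded to 5s, and 15% to 33% with ratings rounded to 10s. The inference holds only for finely graded ratings.

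**Importance.** Temporal summation is one of 16 rows in Table 3, and the documents do not call it a key outcome. The row named for endogenous pain modulation is conditioned pain modulation. No secondary comparison in this pilot is powered.

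**The cut-off in the next row.** The phrase "whereby %CPM ≤ 100 indicated inefficient pain modulation" might suggest the same fault. It does not show one: that index is already continuous, and nothing says it is analysed as a dichotomy.

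**Conclusion.** The point holds as a minor one. The only defined form of temporal summation is a flag on any increase, no named analysis fits it, and the plan does not say which form is analysed. That much rests on the text.

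The size is conditional. If the flag is analysed, scores are normal and 50% to 90% of participants have summation present, the loss is about 36% to 66% of the information at one visit and about 42% to 75% for the comparison of change under the simulated settings. A reader might take such a range as a property of this trial. It is not, because the documents give no prevalence, SD or distribution for the score. Type I error and the primary feasibility conclusion are untouched; the effect is confined to the precision and reading of one exploratory estimate.

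**What to change.** - **Table 3:** define the analysed temporal summation outcome as the rating after 10 stimuli minus the rating after one stimulus, both on the 0-100 scale.
- **Section 2.11:** state that this continuous score is what is compared between arms. Baseline adjustment is optional and is not needed for this fix.
- **The flag:** keep present/absent as a descriptive count at each visit. If it is compared between arms, name a method for binary data, such as a risk difference with its confidence interval or a logistic model.

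No change is needed to the conditioned pain modulation row. The cost is two or three sentences. Both ratings are already collected, so there is no added data collection or participant burden. The wording should be settled before the arms are compared.

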## 2.9. Exit survey and focus group

At follow-up, a satisfaction survey will be conducted. Participants who indicated upon initially consenting to the study that they would like to participate in a focus group will be contacted. Qualitative description will be used to explore participants' experience and perceptions of the feasibility and acceptability of the Pain Informed Movement program as well as the standard treatment as well as the procedure for the entire study. An interview guide developed by patients and practitioners will be used. The focus groups will be conducted virtually consisting of six to eight participants and will last about 60–90 min. The session will be recorded, and transcripts will be produced to ensure accuracy of the responses.

## 2.10. Data integrity

The health information collected in this study will be kept confidential on a secure REDCap platform maintained by McMaster University. To ensure confidentiality, each participant will be given a unique identification number. At the end of the study, the anonymized data will be kept and will comprise a resource database. The researchers and the ethics board may access the study records to monitor the research and verify the accuracy of study information. No records with identifying information will be allowed to leave the principle investigator's office. Study information will be kept for 10 years, then will be permanently destroyed.

## 2.11. Analysis

Descriptive statistics will be used to report feasibility outcomes. The quantitative analysis of secondary outcomes will be by intention-

to-treat principles. Repeated measures analysis of variance (ANOVA) will be used to assess the amount of change in outcome measures and compare them between the two groups using means and 95% CIs. Similarly, within group differences will be analyzed using the paired sample's t-test and will be reported using means and 95% CIs. Where possible we will also report minimally important difference.

The transcripts of the focus group interviews will be analyzed using thematic content analysis to identify suggestions for program modification [46]. Line-by-line reading of the transcripts will be performed and thematic patterns will be explored. Once themes and patterns are identified, each meaningful segment of text will be assigned a conceptual code.

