## **2. Methods**

### **2.1. Study design**

This is a pilot study with a nested qualitative component designed as a parallel, randomized, single-centre, two-arm clinical trial with a 1:1 allocation ratio. Informed consent will be obtained from all participants prior to initiating the study. All participants will be invited to complete an exit survey and take part in focus group interviews at program completion. Fig. 1 depicts the trial design. The procedures will be followed in accordance with the ethical standards of the responsible committee on human experimentation (institutional and national) and with the Helsinki Declaration of 1975, as revised in 2000. The Conceptual Framework for Defining Feasibility [17] and Pilot studies and the Standard Protocol Items: Recommendations for Intervention Trials will be used [18]. Following

program completion, the study results will be reported using the extended CONSORT guideline for pilot trials as well as the TiDIER guidelines [17,19]. The study protocol is registered at [clinic trials.gov #NCT05730829](https://clinicaltrials.gov/ct2/show/NCT05730829).

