## **2.2. Study participants**

Sample size is based on the primary outcome of complete follow-up using the confidence interval method for calculating sample size in pilot trials [20]. We will aim for 90% follow-up but will consider the trial successful if we achieve 81%. To achieve a margin of error of 9%, with 10% added for attrition, we will require 66 participants (n ¼ 33 per arm).

Participants will be recruited through the email lists of the McMaster University's community and research centers and their social media pages. Additionally, the study poster will be placed on other social media channels (e.g., Twitter, Facebook advertisements) and flyers will be placed in local Orthopaedic surgeon, Rheumatologist, and Psychiatrists offices.

The inclusion and exclusion criteria are listed in Table 1.

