### **2.7. Primary and feasibility outcomes**

The primary outcome measure is the follow-up rate (i.e., number of participants that completed the program and attended follow-up). Other feasibility outcomes include: acceptability (content, format, frequency, and duration) of the Pain Informed Movement program compared to the control group, recruitment rate, burden of procedures, adherence rate (i.e., number of participants that attended all in-person sessions), compliance to the program (i.e., number of participants that reported completion of at least three exercise sessions per week), and AEs. A priori success criteria will be used to determine feasibility and acceptability of the programs (Table 2).

Table 2:

*A priori* feasibility criteria.

Outcome	A priori criteria		
	Proceed	Proceed with protocol amendments	Significant amendments required
Follow up	≥90% of participants followed up at 8 weeks	≥50% of participants followed up at 8 weeks	≤50% of participants followed up at 8 weeks
Recruitment	≥40 participants consent to participate/year	≥30 participants consent to participate/year	<30 participants consent to participate/year
Compliance to exercise program	≥80% of participants report exercise at least 3 times a week	≥50% of participants report exercise at least 3 times a week	<50% of participants report exercise at least 3 times a week
Program content acceptability – usefulness	≥50% found treatment useful (Likert ≥4/5)	≥25% found treatment useful (Likert ≥4/5)	<25% found treatment useful (Likert ≥4/5)
Program content acceptability – frequency	≥50% found frequency acceptable (Likert ≥4/5)	≥25% found frequency acceptable (Likert ≥4/5)	<25% found frequency acceptable (Likert ≥4/5)
Program content acceptability – duration	≥50% found duration acceptable (Likert ≥4/5)	≥25% found duration acceptable (Likert ≥4/5)	<25% found duration acceptable (Likert ≥4/5)
Format acceptability – delivery	≥50% found treatment delivery (in-person and home) acceptable (Likert ≥4/5)	≥25% found treatment delivery acceptable (Likert ≥4/5)	<25% found treatment delivery acceptable (Likert ≥4/5)
Adherence to in person treatment	≥75% of participants attended all in person treatment sessions	≥50% of participants attended all in person treatment sessions	≤25% of participants attended all in person treatment sessions

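### The follow-up rate, sized by the confidence-interval method, has no planned interval, and an observed 81% is a success in section 2.2 but not a clean Proceed in Table 2

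*Combined protocol and SAP*

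**What the plan says.** Three places in the combined protocol and SAP bear on how the primary outcome is judged.

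- **Section 2.2 (Study participants).** The basis for the number recruited is given in one sentence: "Sample size is based on the primary outcome of complete follow-up using the confidence interval method for calculating sample size in pilot trials". The next sentence reads "We will aim for 90% follow-up but will consider the trial successful if we achieve 81" per cent, and the one after it "To achieve a margin of error of 9%, with 10% added for attrition, we will require 66 participants", 33 per arm.
- **Section 2.7 and Table 2.** "The primary outcome measure is the follow-up rate (i.e., number of participants that completed the program and attended follow-up"). Table 2 places a result in the Proceed column when "≥90% of participants followed up at 8 weeks", and in the middle column, proceeding with amendments, when "≥50% of participants followed up at 8 weeks". Both are bare observed percentages, and no denominator is named.
- **Section 2.11 (Analysis).** "Descriptive statistics will be used to report feasibility outcomes". The 95% confidence intervals in that section are attached to the between-group and within-group comparisons of outcome measures, not to the feasibility outcomes.

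**The concern.** There are two linked gaps.

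First, the trial's size is justified by how precisely it will estimate one proportion, yet the plan never says that this precision will be reported. The exploratory outcomes are promised intervals and the primary outcome is not. A reader given only a percentage from 66 people cannot see how wide the plausible range is.

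Second, the plan has two different bars for the same quantity. Section 2.2 uses 81% and Table 2 uses 90%. A result between them can be reported as a success or as a need for amendments, depending on which section is cited. Follow-up is the primary outcome and the first row of the progression table, so this ambiguity affects the main conclusion of the pilot.

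**Working it through.** **Inputs.** Target 0.90, margin 0.09, attrition allowance 10%, N = 66 and the 81% figure come from section 2.2. The 90% and 50% bars come from Table 2. The confidence level is not stated for this outcome. Two-sided 95% is assumed, the only level used in section 2.11.

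**The plan's own figure.** The usual precision formula gives n = 1.96² × 0.90 × 0.10 / 0.09² = 42.7, so 43. With attrition this is 43/0.90 = 47.8, so 48. The stated 66 is not reproduced from these inputs at 95%. That is a separate matter. The check below uses the stated N = 66.

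**Where 81% comes from.** 0.90 − 0.09 = 0.81, so the figure matches the lower end of the planned interval around 90%. At the stated N the correspondence is only approximate: with n = 66 and p = 0.90 the Wald half-width is 1.96 × √(0.09/66) = 0.072, giving a lower limit of 82.8%.

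**Counts where the two sections disagree (N = 66).**
- 0.81 × 66 = 53.5, so the section 2.2 bar is first met at 54 (81.8%).
- 0.90 × 66 = 59.4, so the Table 2 Proceed bar is first met at 60 (90.9%); 59/66 is 89.4%.
- Results of 54 to 59 are successful under section 2.2 and in the amendments band under Table 2.

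**Interval at 54/66.** For Wilson, with p = 54/66 and z = 1.96:

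[p + z²/2n ± z√(p(1−p)/n + z²/4n²)] / (1 + z²/n) = (0.8473 ± 0.0975) / 1.0582

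| Method | 95% lower | 95% upper |
|---|---|---|
| Wilson | 70.9% | 89.3% |
| Exact (Clopper-Pearson) | 70.4% | 90.2% |
| Wald | 72.5% | 91.1% |

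**Chance of meeting each bar (exact binomial, N = 66).**

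| True follow-up | P(54 or more) | P(60 or more) | P(54 to 59), the difference |
|---|---|---|---|
| 75% | 12.6% | 0.1% | 12.5% |
| 81% | 50.8% | 2.2% | 48.6% |
| 85% | 81.7% | 11.7% | 70.1% |
| 90% | 98.7% | 50.6% | 48.1% |

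The differences are taken before rounding. If true follow-up equals the 90% target, the result falls in the range with two answers almost half the time.

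**Would a lower-limit rule match Table 2?** Requiring the 95% Wilson lower limit to reach 81% needs 60/66 (lower limit 81.6%; 59/66 gives 79.7%), the same count as Table 2's Proceed bar. This agreement is specific to the sample size. With 60 participants, 54/60 meets 90% but its Wilson lower limit is 79.9%. The two rules also need different counts at 61, 62, 63 and 70. By Wald, 59/66 would pass the lower-limit rule (82.0%) and fail Table 2.

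**The case against.** The strongest reply is that Table 2 already protects the decision. Section 2.7 says its prespecified criteria determine feasibility, and under them 54/66 does not earn a clean Proceed. A reader might infer that the plan would send a trial with follow-up near 71% straight to a definitive study. The documents do not support that: only the sentence in section 2.2 calls 81% a success. This reply stands. It limits the harm, but the two sections still disagree.

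Second, 81% may have been meant as the lower limit around an observed 90%, since the target, the 81% and the margin appear in consecutive sentences. That is plausible. A reader might infer that the authors mistook a lower limit for an observed bar, but the text does not settle this. The wording reads as an observed value, and the plan should say which is meant.

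Third, descriptive statistics do not rule out an interval. That is correct. The gap is that none is specified and nothing in the decision refers to one.

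Fourth, a reader might infer that a result at the 81% bar excludes the 90% target. That holds only by Wilson at 54/66. The exact and Wald upper limits include 90%, and at 55/66 the Wilson upper limit is 90.4%.

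Finally, how strict a pilot's progression bar should be is for the investigators to decide. Nothing in the documents requires a formal lower-limit test. Compared with the 81% bar, such a test would cut the chance of success at a true 90% from 98.7% to 51%.

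**Conclusion.** The concern holds in a limited form. The primary outcome was sized for precision but has no planned interval, and sections 2.2 and 2.7 give different answers for 54 to 59 of 66. At the lowest count that meets the 81% bar, the data are compatible with follow-up of about 71% (70.4% to 72.5% by method), and the upper limit lies close to 90%.

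These figures assume a two-sided 95% level and a denominator of all 66 randomised participants. With 60 in the denominator, 49/60 gives a Wilson lower limit of 70.1%, so the conclusion does not depend on the choice. The finding does not show that the progression decision is unsafe, or that the success rule must become a lower-limit test. It is a modest reporting gap and an inconsistency of criteria, both worth correcting before results are known.

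**What to change.** 1. **Section 2.11.** State that the follow-up rate will be reported as a proportion of all randomised participants, with a 95% Wilson (or exact) confidence interval, and read beside the Table 2 category. Name the method and level.
2. **Section 2.2.** State that the Table 2 bands decide progression, and that 81% is the planned lower confidence limit around a 90% rate (90 minus the 9-point margin), not a separate observed-value success bar.

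The cost is a few sentences, with no extra participants or data. The downside is that an observed 81% can no longer be called an unqualified success.

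A formal requirement that the lower limit reach 81% is optional. If the investigators want it, they should state how it ranks against Table 2, because the two can disagree when the number randomised is not 66.
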